| Evaluate the pharmacokinetics of LY3451838 in healthy subjects following a single dose of LY3451838. | 
 • AUC • C_{max} |

Abbreviations: AUC = area under the concentration-time curve; C_{max} = maximum drug concentration

Summary of Study Design:

Study J1H-MC-LAJA is a first-in-human, investigator- and subject-blind, placebo-controlled, randomized, 2-part study in healthy subjects to evaluate the safety, tolerability, and pharmacokinetics of LY3451838. In Part A, the single ascending doses of LY3451838 will be administered IV in up to 6 cohorts of 8 subjects each. In Part B, a single dose of LY3451838 will be administered SC in up to 2 cohorts of 8 subjects each.

Safety / tolerability, pharmacokinetic, immunogenicity, and exploratory pharmacodynamic assessments will be performed at prescribed time points during the stay at the clinical research unit (CRU) and at subsequent study visits.

All available safety and PK data will be reviewed before each dose escalation. The proposed doses may be adjusted after review of available data from previous dose levels after consultation with a Safety Review Panel (SRP) that is independent of the team.

Treatment Arms and Planned Duration for an Individual Subject:

In both parts, within each cohort, subjects will be randomly assigned to receive LY3451838 or placebo in a 6:2 ratio.

Part A: LY3451838 will be administered IV, at single ascending dose levels, starting at 25 mg and escalated up to 1500 mg.

Part B: LY3451838 will be administered SC as a single dose, which is planned as a 250 mg dose or a dose that matches that of Cohort 3 in Part A. Up to 2 cohorts in Part B may be enrolled to explore various features of SC dosing at the same dose level.

In both parts, subjects will be followed for approximately 20 weeks following administration of the study drug.

Number of Subjects:

Up to 80 healthy subjects may be enrolled so that approximately 6 subjects in each LY3451838 dosing group complete the 20-week study. Any subject who was withdrawn before completion of all study activities may be replaced at the discretion of the Sponsor.

Statistical Analysis:

Safety: The primary safety endpoints are the numbers and types of treatment-emergent serious adverse events and adverse events. Summary statistics for each cohort will be provided by dose level and for all placebo subjects combined.

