5.2 Number of Participants

Up to 80 healthy subjects may be enrolled so that approximately 6 subjects in each dosing group (including that of pooled placebo groups in Part A) complete the study. Subjects who discontinued from the study before study completion may be replaced at the discretion of the sponsor.

A subject completes the study when all scheduled procedures shown in the Schedule of Activities (Section 2) have been finished.

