7.2 Method of Treatment Assignment

In both parts of the study, within each cohort, eligible subjects will be enrolled sequentially, and will be randomly assigned to receive either LY3451838 or placebo in a 6:2 ratio. Treatment assignment will be determined by a computer-generated randomization sequence using an interactive web response system (IWRS).

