### 4.1 Sample Size and Statistical Power Consideration

Up to 80 healthy subjects may be enrolled so that approximately 6 subjects in each LY3451838 dosing group (including that of pooled placebo groups in Part A) complete the 20-week study. Subjects who discontinued from the study completion may be replaced at the discretion of the sponsor.

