## **6. TREATMENT DESCRIPTIONS**

Unless otherwise indicated, on the summary tables, the subjects are to be identified as LY3451838 by each cohort (cohort 1, cohort 2, cohort 3, cohort 4, cohort 5, cohort 6, cohort 7, cohort 8) and all placebo subjects combined, where applicable.

As of the date of data locked for this analysis, there is no patients enrolled in the cohort 8.

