# **9.      ANALYSIS OF SAFETY ENDPOINTS**

## 9.1 Adverse Events

The adverse events will be coded by the Medical Dictionary for Drug Regulatory Activities (MedDRA) version 22.0. The treatment-emergent adverse event (TEAE) is defined as any AE emerging or worsening after start of investigational medicinal product (IMP) administration (including placebo). Summary tables will include number of subjects reporting TEAEs and as percentage of number of subjects for the overall subjects. The number of serious TEAEs will be summarized in the appropriate summary table. Summary tables will also be presented for the frequency of adverse events by the MedDRA system organ class and preferred term. Multiple events in the same system organ class for a subject are only counted once in the statistics of that system organ class. The SOC will be presented alphabetically and preferred term within SOC will be presented in descending order of overall frequency. Summary tables will also be provided for the frequency of adverse events by MedDRA system organ class and preferred term and severity of adverse events, and relationship of adverse events to study drug. In these summaries, the most extreme outcome (highest severity and closest relationship to study drug) will be used for those subjects who experience the same adverse event (per preferred term) on more than one occasion.

The number and percentage of patients with Serious TEAE by SOC and preferred term will be summarized. An individual listing of serious TEAE will also be provided.

The summary tables will be performed by each cohort in LY3451838, overall LY3451838 and all placebo subjects combined.

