	Median	XX.X	XX.X	XX.X	XX.X	XX.X	XX.X	XX.X	XX.X	XX.X
	Minimum	XX	XX	XX	XX	XX	XX	XX	XX	XX
	Maximum	XX	XX	XX	XX	XX	XX	XX	XX	XX

Program: 14.1.2.xxxx.sas

Eli Lilly and Company - PROTOCOL: J1H-MC-LAJA  
 A Safety, Tolerability, and Pharmacokinetics Study of LY3451838 in Healthy Subjects

Table 14.1.2 Demographics and Baseline Characteristics (Safety)

	LY3451838							Placebo	Overall
	Cohort 1 25mgIV N=XX	Cohort 2 75mgIV N=XX	Cohort 3 250mgIV N=XX	Cohort 4 500mgIV N=XX	Cohort 5 1000mgIV N=XX	Cohort 6 1500mgIV N=XX	Cohort 7 250mgSC N=XX		
BMI (kg/m  ) N	XX	XX	XX	XX	XX	XX	XX	XX	XX
Mean	XX.X	XX.X	XX.X	XX.X	XX.X	XX.X	XX.X	XX.X	XX.X
SD	XX.X	XX.X	XX.X	XX.X	XX.X	XX.X	XX.X	XX.X	XX.X
Median	XX.X	XX.X	XX.X	XX.X	XX.X	XX.X	XX.X	XX.X	XX.X
Minimum	XX	XX	XX	XX	XX	XX	XX	XX	XX
Maximum	XX	XX	XX	XX	XX	XX	XX	XX	XX

Program: 14.1.2.xxxx.sas

Eli Lilly and Company - PROTOCOL: J1H-MC-LAJA  
 A Safety, Tolerability, and Pharmacokinetics Study of LY3451838 in Healthy Subjects

Table 14.3.1.1 ¶ Number of Subjects with Treatment-Emergent Adverse Events (Safety)

		LY3451838							Placebo	
		Cohort 1 25mgIV N=XX	Cohort 2 75mgIV N=XX	Cohort 3 250mgIV N=XX	Cohort 4 500mgIV N=XX	Cohort 5 1000mgIV N=XX	Cohort 6 1500mgIV N=XX	Cohort 7 250mgSC N=XX	Total LY N=XX	Placebo N=XX
With At Least One Adverse Event	N	xx	xx	xx	xx	xx	xx	xx	xx	
	Yes	x(xx.x%)	x(xx.x%)	x(xx.x%)	x(xx.x%)	x(xx.x%)	x(xx.x%)	x(xx.x%)	x(xx.x%)	
	No	x(xx.x%)	x(xx.x%)	x(xx.x%)	x(xx.x%)	x(xx.x%)	x(xx.x%)	x(xx.x%)	x(xx.x%)	
With At Least One Mild or Moderate Adverse Event	N	xx	xx	xx	xx	xx	xx	xx	xx	
	Yes	x(xx.x%)	x(xx.x%)	x(xx.x%)	x(xx.x%)	x(xx.x%)	x(xx.x%)	x(xx.x%)	x(xx.x%)	
	No	x(xx.x%)	x(xx.x%)	x(xx.x%)	x(xx.x%)	x(xx.x%)	x(xx.x%)	x(xx.x%)	x(xx.x%)	
With At Least One Severe Adverse Event	N	xx	xx	xx	xx	xx	xx	xx	xx	
	Yes	x(xx.x%)	x(xx.x%)	x(xx.x%)	x(xx.x%)	x(xx.x%)	x(xx.x%)	x(xx.x%)	x(xx.x%)	
	No	x(xx.x%)	x(xx.x%)	x(xx.x%)	x(xx.x%)	x(xx.x%)	x(xx.x%)	x(xx.x%)	x(xx.x%)	
With At Least One Serious Adverse Event	N	xx	xx	xx	xx	xx	xx	xx	xx	
	Yes	x(xx.x%)	x(xx.x%)	x(xx.x%)	x(xx.x%)	x(xx.x%)	x(xx.x%)	x(xx.x%)	x(xx.x%)	
	No	x(xx.x%)	x(xx.x%)	x(xx.x%)	x(xx.x%)	x(xx.x%)	x(xx.x%)	x(xx.x%)	x(xx.x%)	
With At Least One Not Related Adverse Event	N	xx	xx	xx	xx	xx	xx	xx	xx	
	Yes	x(xx.x%)	x(xx.x%)	x(xx.x%)	x(xx.x%)	x(xx.x%)	x(xx.x%)	x(xx.x%)	x(xx.x%)	
	No	x(xx.x%)	x(xx.x%)	x(xx.x%)	x(xx.x%)	x(xx.x%)	x(xx.x%)	x(xx.x%)	x(xx.x%)	
With At Least One Related Adverse Event	N	xx	xx	xx	xx	xx	xx	xx	xx	

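### Minor, cheap improvement: the AE tables set the only SC cohort beside one placebo column planned as 12 IV and 2 SC subjects; add placebo counts by route

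*SAP*

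**What the plan says.** - **Allocation.** Protocol 7.2: within each cohort, subjects are "randomly assigned to receive either LY3451838 or placebo in a 6:2 ratio". The placebo subjects in Part B are dosed SC (Protocol 5.1.2).
- **Pooling.** The protocol synopsis sets the display: "Summary statistics for each cohort will be provided by dose level and for all placebo subjects combined". Protocol 10.3.1 says the same for AEs and SAEs. SAP 6 and SAP 9.1 follow it; the SAP 9.1 sentence is "The summary tables will be performed by each cohort in LY3451838, overall LY3451838 and all placebo subjects combined".
- **Shells.** Tables 14.3.1.1 to 14.3.1.3 in SAP 13 have columns for Cohorts 1 to 7, total LY3451838 and one placebo group. No AE table divides placebo by route.
- **Cohorts.** SAP 6 records that "there is no patients enrolled in the cohort 8", so Cohort 7 (250 mg SC) is the only SC cohort.
- **Injection-site reactions.** Protocol 9.2 has them recorded as AEs with extra descriptors. Protocol 10.3.1 includes them among the safety assessments to be listed and summarised.

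**The concern.** The controls that randomisation gives Cohort 7 are its own placebo subjects, about two of them. Only these show what the SC injection does without drug. In the AE tables they are merged with 12 subjects who had an infusion and no SC injection. An event caused by the injection can then appear in Cohort 7 and look almost absent under placebo, with no drug effect at all.

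An injection-site preferred term tells the reader that route is involved, although the placebo percentage is still taken over all 14. The any-event rows of Tables 14.3.1.1 and 14.3.1.2 give no such cue.

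What is at stake is how one cohort reads on the primary (safety) endpoint. No hypothesis test, dose or endpoint depends on it.

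**Working it through.** The plan states no placebo N (the shells show N=XX), so there is no figure to reproduce. The counts below are the planned ones, without replacements.

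**1. Column make-up**
- Placebo: 6 IV cohorts × 2 = 12; 1 SC cohort × 2 = 2; total 14.
- LY3451838: 6 × 6 = 36 IV; 1 × 6 = 6 SC; total 42.
- SC share: 6/42 = 14.3% and 2/14 = 14.3%, so total LY3451838 against placebo is balanced by route.
- Cohort 7 is 6/6 SC and is compared with a column that is 2/14 SC.

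**2. Injection-site rows**

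IV subjects have no SC injection, so the pooled placebo rate is at most 2/14 = 14.3%, even if both SC placebo subjects react.

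Illustration with no drug effect: suppose 4 of the 8 Part B subjects react. The expected split is 4 × 6/8 = 3 in Cohort 7 and 4 × 2/8 = 1 in placebo. The chances of 0, 1 or 2 placebo reactors are hypergeometric: 15/70, 40/70 and 15/70.

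| SC placebo reactors | Probability | Cohort 7 | Pooled placebo | SC placebo |
|---|---|---|---|---|
| 0 | 0.21 | 4/6 = 66.7% | 0/14 = 0.0% | 0/2 |
| 1 | 0.57 | 3/6 = 50.0% | 1/14 = 7.1% | 1/2 |
| 2 | 0.21 | 2/6 = 33.3% | 2/14 = 14.3% | 2/2 |

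With 4 reactors, the pooled comparison favours placebo whichever way chance falls.

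**3. Any-TEAE row**

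Let b be the background event rate, p the rate of events caused by SC administration and q the rate caused by IV administration. Take these as independent and the same on drug and placebo. The documents give none of the three.

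- Cohort 7: b + (1−b)p
- Pooled placebo: (12/14)[b + (1−b)q] + (2/14)[b + (1−b)p]
- Spurious gap: (12/14)(1−b)(p−q)

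One Cohort 7 subject is 1/6 = 16.7 points. Multiplying the gap by 6 expresses it in subjects.

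| b | p | q | Gap | Subjects |
|---|---|---|---|---|
| 40% | 25% | 0 | 12.9 points | 0.77 |
| 40% | 25% | 10% | 7.7 points | 0.46 |
| 60% | 10% | 0 | 3.4 points | 0.21 |
| 20% | 50% | 0 | 34.3 points | 2.06 |

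The gap reaches one subject only if p−q is at least (1/6)(14/12)/(1−b) = 0.194/(1−b). That is 24%, 32% and 49% at b = 20%, 40% and 60%. If q exceeds p, the gap changes sign.

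**4. What an SC-placebo column can show**

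Exact 95% limits: 0/2 gives 0 to 84.2%, 1/2 gives 1.3 to 98.7%, and 2/2 gives 15.8 to 100%.

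**The case against.** The strongest reply is that this is a choice of display. Pooling is set in the protocol and repeated in the SAP, and the study is descriptive. Cohort 7 is labelled as SC and stands in the same table as the 250 mg IV cohort. An injection-site term announces its own route, and a column of two subjects can mislead as easily as a diluted one. Infused placebo subjects can also have administration-related events, which narrows the any-TEAE gap.

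Most of this stands. It rules out calling the pooling an error, keeps the point minor and is the reason q is in the formula. It does not remove the dilution. The 250 mg IV cohort matches dose but had no SC injection, so it cannot stand in for SC placebo. Raw counts of two subjects show how little is known, whereas 1/14 hides it.

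A reader might infer two stronger points that the documents do not support:

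- **That the SAP fails a protocol commitment on injection-site reactions.** Protocol 10.3.1 has them listed and summarised; it does not promise a separate table. As AEs they enter the tables by preferred term, severity and relationship, and Listing 11. What the SAP leaves unsaid is only where the Protocol 9.2 descriptors will appear. The lack of a listing shell proves little, since no listing has one.
- **That a Part A placebo group was promised as a display.** Protocol 5.2 aims that "approximately 6 subjects in each dosing group (including that of pooled placebo groups in Part A) complete the study", and SAP 4.1 repeats the phrase. This is sample-size wording about completers and does not define a reporting group.

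**Conclusion.** The point holds as a minor, cheap improvement. The planned AE tables never show the only SC cohort beside its own route-matched randomised controls. This affects the reading of the Cohort 7 column; the total LY3451838 comparison is balanced by route.

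The firm part is arithmetic. On planned numbers the pooled placebo injection-site rate is capped at 14.3%, and the expected no-effect case with 4 reactors reads 50.0% against 7.1% instead of 3/6 against 1/2. The any-TEAE effect is softer. With q = 0 it runs from 0.2 to 2.1 subjects over b = 20–60% and p = 10–50%, and it shrinks as q rises towards p. In many of these settings it is under one subject.

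The counts assume 2 placebo subjects per cohort, Cohort 8 empty and no replacements.

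**What to change.** Keep the combined placebo column. Add 'Placebo IV' (Part A) and 'Placebo SC' (Part B) columns, shown as counts (n/N), to the overall and SOC/PT AE tables, numbered 14.3.1.1 to 14.3.1.4 in the SAP 12.1 table list. The shells in SAP 13 use 14.3.1.4 for the severity table, so cite the table titles as well. Footnote that SC placebo is about 2 subjects and that the display cannot establish or exclude a drug effect.

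The cost is two columns in four tables, from data already collected, documented by the change request or note-to-file that SAP 2 provides for, and in the CSR. The downside is that the SC-placebo column can show only 0, 1 or 2 of 2 and could be over-read; the counts and the footnote limit that.

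Optional clarification: one line naming the Protocol 9.2 injection-site descriptors as fields of Listing 11.

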## 9.2 Vital Signs

Vital signs (systolic and diastolic blood pressure, pulse rate and body temperature) are to be summarized at each visit. Change from baseline to each post-baseline visit will also be provided. When triplicate blood pressure or pulse rate measurement precede the orthostatic measurement, the last supine blood pressure or pulse rate measurement will be used.

### 9.3 Laboratory Tests

The test results of clinical chemistry, hematology and urinalysis are to be summarized by visit. Change from baseline to each post-baseline visit will also be provided. When applicable, all the test result in the following list will be presented.

Clinical Chemistry:	Hematology:
Alkaline phosphatase	Erythrocytes count (RBC)
Alanine Aminotransferase	Hematocrit
Aspartate Transaminase	Hemoglobin
Albumin	Mean cell volume
Blood urea	Mean cell hemoglobin
Bicarbonate	Mean cell hemoglobin concentration
Total Bilirubin	Leukocyte count (WBC)
Calcium	Platelets
C-reactive Protein	Basophils
Complement 3	White blood cell count + differential
Complement 4	Erythrocyte sedimentation rate (ESR)
Sodium	
Total cholesterol	Urinalysis:
Chloride	pH
Creatinine	Specific gravity
Glucose	Blood
Potassium	Nitrite
	Bilirubin
	Ketones
	Protein
	Glucose
	Urobilinogen
	Leukocytes
	Microscopy

Additional analysis will be performed to C3, C4, CRP and ESR.

The number and percentage of subjects with significant decrease in C3 and C4 will be summarized at each of the scheduled visits by treatment and by cohort.

The number and percentage of subjects with significant increase in CRP and ESR will be summarized at each of the scheduled visits by treatment and by cohort.

The significant decrease in C3/C4 will be met if the lab result is classified as NORMAL at baseline, and classified as LOW (<LLN) at post-baseline visits, OR the lab result is classified as LOW at baseline(<LLN), and result gets LOWER than baseline at post-

baseline visits. The significant increase in CRP/ESR will be met if the lab result is classified as NORMAL at baseline, and classified as HIGH ( $>\text{ULN}$ ) at post-baseline visits, OR the lab result is classified as HIGH at baseline( $>\text{ULN}$ ), and result gets HIGHER than baseline at post-baseline visits.

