16. Have an abnormality in the 12-lead ECG that, in the opinion of the investigator, increases the risks associated with participating in the study. In addition, subjects with the following findings will be excluded:

- a. Confirmed Fridericia's corrected QT (QTcF) interval >450 msec for men and >470 msec for women. One additional ECG may be performed if necessary
17. Show evidence of human immunodeficiency virus (HIV) and/or positive human HIV antibodies, hepatitis C and/or positive hepatitis C antibody, or hepatitis B and/or positive hepatitis B surface antigen
18. Have donated blood of more than 450 mL or have participated in a clinical study that required similar blood volume drawn within the past 3 calendar months.
19. Are unwilling to stop alcohol consumption while resident in the CRU.
20. Have an average weekly alcohol intake that exceeds 21 units per week for male subjects and 14 units per week for female subjects (1 unit = 12 oz or 360 mL of beer; 5 oz or 150 mL of wine; 1.5 oz or 45 mL of distilled spirits)
21. Are a current smoker of more than 10 sticks of cigarettes or the equivalent of other tobacco products per day and are unable/unwilling to stop smoking tobacco products while resident in the CRU. Heavy smokers as per judgment of the investigator should be excluded from the study
22. Have an abnormal blood pressure (supine) defined as diastolic blood pressure >90 or <60 mmHg and/or systolic blood pressure >140 or <90 mmHg; or with minor deviation judged to be acceptable by the investigator. Retesting may occur once during the screening visit within 2 hours of the initial abnormal blood pressure measurement at the discretion of the investigator
23. Have clinically significant proteinuria or hematuria at screening and enrollment
24. Regularly use known drugs of abuse
25. Have received treatment with biologic agents (such as monoclonal antibodies, including marketed drugs) within 3 months or 5 half-lives (whichever is longer) prior to dosing.
26. Have significant allergies to monoclonal antibodies, common antihistamines, epinephrine; or have significant allergies or intolerance to methylprednisolone or other systemic corticosteroids.
27. Have clinically significant multiple or severe drug allergies, or intolerance to systemic and topical corticosteroids, or severe post treatment hypersensitivity reactions (including, but not limited to, erythema multiforme major, linear IgA dermatosis, toxic epidermal necrolysis, or exfoliative dermatitis)

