9.4.5.2 Hypersensitivity reactions

Acute and serious hypersensitivity reactions will be assessed and managed as clinically indicated. The clinical information, including examination findings, laboratory testing and treatment for all serious adverse events, including hypersensitivity reactions, will be captured in the EDC.

Non-acute hypersensitivity reactions, including type 3 hypersensitivity reaction will be assessed by clinical presentation. Routine monitoring of vital signs with regular physical examinations, and laboratory testing (including hematology, liver and renal testing, complements C3 and C4, c-reactive protein [CRP] and erythrocyte sedimentation rate [ESR], and urine analysis) will be undertaken to assess for the development of vasculitis, serum sickness and other manifestations of type 3 hypersensitivity reactions.

Stored serum samples for possible immune safety laboratory testing (including, but not limited to: β -tryptase, total IgE, immune-complex testing, and cytokine panel) will be collected for all subjects before study drug administration (Section 2). Additional, unscheduled, stored serum samples for possible immune safety laboratory testing should also be collected approximately 60 to 120 minutes and 4 to 6 weeks after moderate or severe infusion reactions or hypersensitivity reactions.

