## **7. STATISTICAL ANALYSIS METHODS AND ISSUES**

### **7.1 Statistical Methods**

Descriptive statistics, namely sample size (n), mean, standard deviation, median, minimum and maximum for continuous variables, count and percentage for categorical variables, are to be provided.

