## **9.4    Electrocardiogram**

Descriptive statistics of ECG parameters(quantitative) and assessments (qualitative) will be summarized at each visit. The change from baseline will be summarized as well for quantitative parameters at each visit. Shift tables from baseline will be presented for ECG qualitative assessment.

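### SAP 9.3 plans no shift or treatment-emergent summary for urine protein and blood, and does not say how change from baseline applies if these results are categorical

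*SAP*

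**What the plan says.** Protocol 9.4.5.2 describes routine monitoring by vital signs, physical examination and laboratory tests, the last including hematology, liver and renal tests, C3, C4, CRP, ESR and urine analysis. This monitoring "will be undertaken to assess for the development of vasculitis, serum sickness and other manifestations of type 3 hypersensitivity reactions".

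SAP 9.3 treats the three laboratory panels alike. Chemistry, hematology and "urinalysis are to be summarized by visit. Change from baseline to each post-baseline visit will also be provided". It continues: "When applicable, all the test result in the following list will be presented". The urine part of that list holds pH and specific gravity next to protein, blood, nitrite, ketones and others. Under SAP 7.1 the default summary is "count and percentage for categorical variables, are to be provided".

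Two other groups of results get more:

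- SAP 9.3: "Additional analysis will be performed to C3, C4, CRP and ESR". The rule is tied to baseline. A subject counts if the result moves from normal to outside the limit in the direction of concern, or was already outside and gets worse.
- SAP 9.4 keeps change from baseline to the quantitative ECG parameters and adds: "Shift tables from baseline will be presented for ECG qualitative assessment".

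The only urinalysis table listed in SAP 12.1 is 14.3.4.3, and SAP 13 shows no shell for it. Listing 8.3 gives urinalysis by subject and visit.

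**The concern.** Protocol 3.3 names vasculitis as the dose-limiting toxicity in monkeys, and Protocol 3.2 says that it had no clinical signs in the animals. A laboratory sign is therefore worth tabulating in its own right.

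If protein and blood are reported as categories (negative, trace, 1+ and so on), subtraction is undefined and SAP 9.3 offers nothing in its place. What remains is counts and percentages by visit, and these do not link a subject's later result to that subject's baseline.

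Entry rules do not guarantee a clean baseline. Criterion 23 excludes subjects who "Have clinically significant proteinuria or hematuria at screening and enrollment", and criterion 4 accepts laboratory deviations that the investigator judges not clinically significant. A subject with a minor positive can therefore enter, and a later table would mix old and new positives.

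**Working it through.** The documents give no figure on this point, so there is nothing to reproduce. The check asks what counts by visit can and cannot show.

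**Inputs**
- Cohort size on LY3451838: 6, from the 6:2 allocation (SAP 4).
- Baseline: Visit 3 predose, or Visit 2 if Visit 3 is not available (SAP 7.5). The schedule shows no urinalysis at Visit 3, so Visit 2 applies. Footnote d waives some repeat tests when screening is recent, but urinalysis is not among them, so a baseline should exist.
- Post-baseline urinalysis: Visits 4, 6, 8 and 10 as the schedule reads in the text available, so four visits. Columns may have shifted in extraction.
- Numbers of positives: assumed for illustration. The documents give none.

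**One visit.** Let n be the subjects, b the number positive at baseline and f the number positive at a later visit. The number newly positive at that visit lies between max(0, f − b) and min(f, n − b).

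| n | b | f | Lowest | Highest |
|---|---|---|---|---|
| 6 | 0 | 1 | max(0, 1) = 1 | min(1, 6) = 1 |
| 6 | 1 | 1 | max(0, 0) = 0 | min(1, 5) = 1 |
| 6 | 1 | 2 | max(0, 1) = 1 | min(2, 5) = 2 |
| 6 | 2 | 2 | max(0, 0) = 0 | min(2, 4) = 2 |

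In the second row the same table fits 0/5 = 0% or 1/5 = 20% of the subjects at risk. In the first row, with no baseline positives, the count is exact.

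**Four visits.** Suppose 1 of 6 is positive at each of the four post-baseline visits.
- None positive at baseline: it may be the same subject each time or four different subjects, so 1 to 4 subjects were ever newly positive.
- One positive at baseline: that subject may account for all four results, or for none of them, so 0 to 4 were ever newly positive.

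So even with a clean baseline, counts by visit do not give the number of subjects affected over follow-up. The same holds for worsening, which needs each subject's baseline and later grade side by side.

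**Repeat results.** SAP 7.4 keeps only the latest result within a visit. A positive followed by a negative repeat at that visit drops out of the table.

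**The case against.** The case for leaving the text alone has several parts.

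- **The scale is not stated.** Neither document gives a urinalysis method or grading. A reader might infer that the planned change from baseline is impossible for these tests, but the documents do not say that the results are dipstick grades. Numeric change is valid for pH and specific gravity, and the SAP limits presentation to what is applicable. This stands, so the point is conditional. The qualifier, however, supplies no alternative method for categorical results.
- **Urine is not the only test without an event rule.** One might read Protocol 9.4.5.2 as a five-test screen from which the SAP left out one. It also lists hematology, liver and renal tests, which get no event rule either, and it says that non-acute reactions will be assessed by clinical presentation. That stands. The argument for urine is that its results may not fit the summary prescribed.
- **Findings would not be lost.** A reader might infer that new proteinuria or hematuria would go unreported. The documents do not support that. Listing 8.3, or raw-data listings in its place, would show each subject's results. The protocol's adverse event definition includes abnormal laboratory findings, so a reported finding would appear in the TEAE tables. Stopping rule 4 in Protocol 7.4.1.1 also covers laboratory findings and works independently of the SAP. What remains is that listings give no counts by group and the adverse event route depends on investigator reporting.
- **Baseline positives should be few.** Criteria 4 and 23 point that way, so counts at a single visit will often be close to the new positives at that visit. This narrows the single-visit problem but leaves the count across visits unresolved.

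**Conclusion.** SAP 9.3 does not provide the count a safety reader would want: how many subjects in each group developed new or worsened urine protein or blood. Nor does it define change from baseline for categorical urine results. The conclusion rests on the assumption that these results are categorical. If the laboratory reports protein and blood as numbers, change from baseline can be computed and only the missing treatment-emergent count remains.

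The size is minor to moderate and concerns reporting only. The study is descriptive and not powered for hypothesis tests, and no endpoint, population or sample size is affected. It would be tempting to put a trial-wide number on the ambiguity, for example one unclassifiable subject in each of the seven cohorts in the table shells. No document supports an assumed rate of baseline positives, so the figures above only illustrate what such counts can hide.

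**What to change.** In SAP 9.3:

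1. State the reporting scale of each urine test, and limit numeric change from baseline to the quantitative ones, such as pH and specific gravity.
2. For categorical urine tests, present in Table 14.3.4.3 a shift from baseline (Visit 2) to the worst post-baseline category. State that unscheduled and repeat results count here, as an exception to the latest-result rule in SAP 7.4.
3. For protein and blood, add the number and percentage of subjects with a new or worsened result, with the grade shown, by cohort, total LY3451838 and pooled placebo. The denominator is subjects with a baseline and at least one post-baseline result.

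The cost is a short SAP revision and one table shell, using data already collected. The downside is that isolated trace results will be counted, which is why the grade should be shown. The change is to tabulation only and sets no clinical rule.
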